### **Continuous monitoring of BP**

SBPday, SBPnight, SBP24h, DBPday, DBPnight, and DBP24h (mmHg) will be summarized for the Safety population by treatment group at each applicable visit (Day -1 to Day 0, Day 6 to Day 7, and Day 13 to Day 14) by descriptive statistics (n, mean, SD, median, and range). In addition, at each visit after baseline, change from baseline will be calculated and summarized by descriptive statistics (n, mean, SD, median, and range). Baseline will be Day -1 to Day 0.

### **Orthostatic hypotension evaluation**

The orthostatic hypotension evaluation BP values will be summarized for the Safety population by treatment group at each applicable visit (Day 0, Day 7, and Day 14) by descriptive statistics (n, mean, SD, median, and range). In addition, at each visit after baseline, change from baseline will be calculated and summarized by descriptive statistics (n, mean, SD, median, and range). Baseline will be Day 0. The above analysis will be performed for each of the following:

1. Average BP after 5 minutes rest in supine position (average of 3 recordings)
  - a. SBP
  - b. DBP
2. BP 1 minute after standing
  - a. SBP
  - b. DBP
3. BP 3 minutes after standing
  - a. SBP
  - b. DBP
4. Difference between average BP after 5 minutes rest supine and BP 1 minute after standing
  - a. SBP
  - b. DBP
5. Difference between average BP after 5 minutes rest supine and BP 3 minutes after standing
  - a. SBP
  - b. DBP

Comparisons of the orthostatic hypotension BP measurements among treatment arms using ANCOVA will be presented for each of the above 5 parameters. The change from baseline to Day 14 will be considered.

The number and the percentage of patients with evidence of Orthostatic Hypotension (Yes, No, Missing) will be presented at each visit (Day 0, Day 7, and Day 14) by treatment group. The Chi-Squared/Fisher's Exact test will be provided to test differences between arms.

### **Laboratory parameters**

Hematology, chemistry and urinalysis (including urine microscopy) parameters will be summarized for the Safety population by treatment group at each applicable visit (Initial Screening Visit, Day 0\*,

Day 7\*, and Day 14) by descriptive statistics as appropriate (i.e., n, mean, SD, median, and range for continuous data and frequency for categorical data). In addition, at each visit after baseline, change from baseline will be calculated and summarized for continuous data by descriptive statistics (n, mean, SD, median, and range). Baseline will be Day 0 if available, otherwise, the Initial Screening Visit assessment will be used.

\*The laboratory parameters on Day 0 and Day 7 were limited to serum chemistry tests (i.e., no hematology or urinalysis), and further, the serum chemistry tests at Day 7 were limited to creatinine (and calculation of creatinine clearance) and electrolytes (sodium, bicarbonate, calcium, chloride, phosphorous, and potassium).

Shift tables presenting the number and the percentage of patients in each bivariate category (Baseline versus Day 14) with regards to reference range (Low, Normal, High, missing) will be provided for all laboratory parameters by treatment group. Baseline will be Day 0 if available, otherwise, the Initial Screening Visit assessment will be used.

The laboratory reference range for assigning low “L” flags to the creatinine clearance results differed for the Celerion, Belfast laboratory ( $>90$  mL/min) versus the centralized laboratory used for the remaining sites (ACM Global Central Laboratories;  $\geq 60$  mL/min). The serum chemistry shift table analysis will be based on the laboratory assigned flags (i.e., no reassignment of the Celerion, Belfast laboratory flags based on the ACM laboratory reference range will be made). The main body of the clinical study report will note the difference in the creatinine clearance reference range for the two laboratories and will note by treatment group any cases where a Celerion, Belfast low creatinine clearance value would be reassigned as Normal if the  $\geq 60$  mL/min criterion was used.

For serum creatinine and BUN, comparisons between treatment groups will be performed with an ANCOVA model with change from baseline to Day 14 as dependent variable, treatment as fixed effect and baseline as covariate. The number of patients and the number of patients considered in the model will be provided by treatment. P-values of the fixed effects and covariates will also be presented. The adjusted means for treatments and the relative 95% CIs will be presented. The difference between the adjusted means of the three treatment groups will be calculated with the relative 95% CI and p-value.

The primary comparison will be treatment group 1 compared to treatment group 2, and the key secondary comparison will be treatment group 1 compared to treatment group 3. In these analyses, the null hypothesis will be that there is no statistically significant difference in the change in the measured blood parameter (serum creatinine or BUN) from baseline to the end of treatment between the two treatment groups. Baseline will be Day 0 if available, otherwise, the Initial Screening Visit assessment will be used.

The listings and summary tables will use the clinical laboratory test names as they appear in the Study Data Tabulation Model dataset files (i.e., the Clinical Data Interchange Standards Consortium compliant clinical laboratory test names). Refer to “Note to File - Differences in Laboratory Test Names Between Testing Laboratory and Study Data Tabulation Model (SDTM) Files”, a copy of which is available in the Trial Master File.

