21. Asthma, acute rhinitis, nasal polyps, angioneurotic oedema, urticaria or other allergic type reactions after taking acetylsalicylic acid or NSAIDs including cyclooxygenase-2 (COX-2) inhibitors;
22. Subjects who, in the opinion of the Investigator, are unable or unlikely to comply with the dosing schedule and study evaluations;
23. Pregnant or lactating;
24. Unable to correctly use ABPM after instruction on its use;
25. Subjects with Child-Pugh Class B or C cirrhosis;
26. Subjects currently taking a calcium channel blocker or any NSAID for any reason will be excluded. Subjects will not be withdrawn from these drugs to be enrolled in the trial;
27. Subjects that took a calcium channel blocker in the past for any indication;
28. Creatinine clearance < 50 ml/min as estimated by the Cockcroft-Gault equation*;

**Cockcroft-Gault equation:*

estimated creatinine clearance = (140 – age) X body weight (kg)/72 X P_{Cr} (mg/dL)

multiply by 0.85 for women

29. Known cytochrome P450 2C9 (CYP2C9) poor metabolizer;
30. Subjects with allergy or hypersensitivity to sulfonamides.

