**j. Hematology, serum chemistry, and urinalysis**

For the majority of the hematology, serum chemistry, and urinalysis tests, the comparisons of the safety population data among treatment arms using Chi-square, binomial, and logistic analyses for dichotomous variables (e.g., negative/positive) and ANCOVA for continuous variables will not be done due to the limited number of subjects. The exceptions are serum creatinine and blood urea nitrogen (BUN), where comparisons between treatment arms will be performed using an ANCOVA model with change from baseline to Day 14 as the dependent variable, treatment as the fixed effect, and baseline as the covariate.

The laboratory reference range for assigning low "L" flags to the creatinine clearance results differed for the Celerion, Belfast laboratory (>90 mL/min) versus the centralized laboratory used for the remaining sites (ACM Global Central Laboratories;  $\geq 60$  mL/min). The serum chemistry shift table analysis will be based on the laboratory assigned flags (i.e., no reassignment of the Celerion, Belfast laboratory flags based on the ACM laboratory reference range will be made). The main body of the clinical study report will note the difference in the creatinine clearance reference range for the two

laboratories and will note by treatment group any cases where a Celerion, Belfast low creatinine clearance value would be reassigned as Normal if the  $\geq 60$  mL/min criterion was used.

Documentation of the differing creatinine clearance reference ranges for ACM and Celerion, Belfast is included in Appendix 16.1.10 of the clinical study report and in the individual subject laboratory reports that are included with the consolidated case report form PDF files, copies of which are included in the Trial Master File.

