As subjects were enrolled, the Investigator was to take the next sequential kit number in the block provided and assign it to the subject. Due to the issues with labeling noted above (resulting in gaps in available kit numbers), the kit numbers were assigned sequentially, but were not necessarily consecutive. Further, due to the variation in the number of kits initially sent to each site (ranging from 5 to 21), the initial shipment may have included less than a full block or up to two full blocks and two partial blocks.

The Investigational sites were to be re-supplied in the same fashion (i.e., 5 patient kits); however, to accommodate differences in enrollment rate, the number of kits in the resupply shipments ranged from 2 to 10, with each shipment containing sequential randomization numbers. The Investigator was to take the next sequential kit number in the resupply shipment and assign it to the subject. The

sequential numbers were not necessarily consecutive due to the labeling issue noted above. At the end of the study, any unused kits were returned to the distributor.

Subjects were to be randomized 3:3:1, however, the final overall randomization was 6:6:1. The difference is attributed to 1) the labeling issues noted above that led to gaps in the available kit numbers, 2) the distribution of the kits in sequential order from lowest to highest available kit number, 3) the number of kits shipped initially and as re-supply, and 4) only using some of the kits shipped as fewer subjects were enrolled than kits shipped.

As both the primary and secondary efficacy endpoints are based on comparisons of treatment arms 1 and 2, and the ratio of these two arms are similar under a 3:3:1 and a 6:6:1 randomization, this difference from the planned randomization is not anticipated to impact the trial outcomes. A site-specific analysis of the primary endpoint will be done (see Section 1.3.13) to evaluate for any impact that variation in the randomization ratio across sites may have on the outcome.

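### The by-arm creatinine-clearance shift table mixes a >90 mL/min limit at Belfast with a ≥60 mL/min limit elsewhere, so Low has two meanings in one table

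*SAP*

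**What the plan says.** SAP 1.3.9(j) and SAP 7.9 (Laboratory parameters) treat this point in the same terms. They record that the Low "flags to the creatinine clearance results differed for the Celerion, Belfast laboratory (>90 mL/min) versus the centralized laboratory used for the remaining sites", the latter being "ACM Global Central Laboratories; $\geq 60$ mL/min". They then fix the basis of the table: "The serum chemistry shift table analysis will be based on the laboratory assigned flags", and add that "no reassignment of the Celerion, Belfast laboratory flags based on the ACM laboratory reference range will be made".

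The layout is given in SAP 7.9: "Shift tables presenting the number and the percentage of patients in each bivariate category (Baseline versus Day 14) with regards to reference range", with categories Low, Normal, High and missing, by treatment group. No split by laboratory is mentioned.

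The SAP also plans a disclosure. The main body of the study report will state that the two ranges differ and "will note by treatment group any cases where a Celerion, Belfast low creatinine clearance value would be reassigned as Normal" if the ≥60 mL/min limit were used.

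**The concern.** A shift table is read by comparing counts of subjects who crossed a limit, arm against arm. Here the limit depends on the site. The same change in clearance can be a Normal-to-Low shift at Belfast and no shift elsewhere, or the reverse, and the table adds the two together.

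Creatinine clearance matters in this trial. Renal function is in the study title, SAP 6.4 makes clearance a safety endpoint as well as a secondary efficacy endpoint, and the celecoxib label reproduced in the protocol warns of renal toxicity. I found no other planned table that classifies subjects by clearance: SAP 1.3.9(j) drops the between-arm laboratory comparisons except for serum creatinine and BUN.

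**Working it through.** The plan states no figure to reproduce, so the check applies its two rules to the same values.

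**Rules.** Belfast: Normal if >90 mL/min, otherwise Low. Central laboratory: Normal if ≥60 mL/min, otherwise Low. Both come from SAP 1.3.9(j) and 7.9.

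| Baseline to Day 14 (mL/min) | Belfast rule | Central rule |
|---|---|---|
| 95 to 80 | Normal to Low | Normal to Normal |
| 80 to 55 | Low to Low | Normal to Low |
| 80 to 75 | Low to Low | Normal to Normal |
| 80 to 95 | Low to Normal | Normal to Normal |
| 55 to 75 | Low to Low | Low to Normal |
| 95 to 55 | Normal to Low | Normal to Low |
| 100 to 95 | Normal to Normal | Normal to Normal |
| 55 to 52 | Low to Low | Low to Low |

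The first five rows land in different cells; the last three do not. Rows 1 and 2 go in opposite directions: the Belfast rule adds a Normal-to-Low shift in one and loses one in the other.

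**What the planned note can catch.** A Belfast Normal is above 90, so it is also at least 60. The only possible reclassification is Low to Normal, and the note covers exactly that. For the 80-to-55 subject the note should report the baseline of 80. It works value by value, however, and nothing requires the pair to be re-tabulated as a Normal-to-Low shift.

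**Can subjects lie between 60 and 90?** The only clearance bar to entry is "Creatinine clearance < 50 ml/min as estimated by the Cockcroft-Gault equation" (Protocol 4.2), with ages 40 to 75 and weight from 55 kg. Two hypothetical subjects, with assumed characteristics, by the Cockcroft-Gault formula in Protocol 7.3:

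- Man, 60 years, 85 kg, creatinine 1.1 mg/dL: (140 − 60) × 85 / (72 × 1.1) = 85.9 mL/min.
- Woman, 65 years, 75 kg, creatinine 0.9 mg/dL: (140 − 65) × 75 / (72 × 0.9) × 0.85 = 73.8 mL/min.

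Both are Low at Belfast and Normal elsewhere. They show that the band is reachable, not how often it occurs.

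**Illustrative size at Belfast.** The documents give no clearance distribution, so a simulation assumed a normal baseline with mean 85 to 115 and SD 20 to 30, truncated at 50, and a change with mean 0 and SD 8 to 12 mL/min. Across these settings:

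- Low at baseline: 10% to 58% by the Belfast rule, 0.2% to 9% by the central rule.
- Day 14 value of 60 to 90, flagged Low at Belfast: 12% to 49%.
- Normal-to-Low by the Belfast rule although still at or above 60: 3% to 9%.
- Falls from ≥60 to <60: 0.3% to 6.6% of subjects, of which 96% to 100% appear as Low-to-Low.

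For scale only, take 14 subjects, the size of Belfast's first kit shipment (SAP 3.2), which is not its enrolment. The extra Normal-to-Low shifts would number 14 × 0.034 = 0.5 to 14 × 0.090 = 1.3, and the masked falls 14 × 0.003 = 0.04 to 14 × 0.066 = 0.9.

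**The case against.** The best defence is that the SAP saw the problem and disclosed it. The note is in the main body of the report, is by treatment group, and covers every Belfast value that could change category. That stands, and it answers any complaint that reclassified values would go unreported. It does not supply a table with one meaning of Low; a reader would have to rebuild the shifts by hand.

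The second defence is that little depends on the table. Clearance is summarised numerically at each visit and as change (SAP 7.9), tested between arms as a secondary endpoint (SAP 7.8), and accompanied by a baseline-adjusted ANCOVA of serum creatinine (SAP 7.9). None of these uses the flags, all CRF data are listed, and clinically significant laboratory abnormalities are reported as adverse events (SAP 6.4). This also stands and limits the weight of the point. Means do not, however, show who crossed a limit, which is the purpose of a shift table.

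Third, Protocol 10.4 asks for summaries against laboratory normal ranges, and laboratory flags comply with that. This is a reason to keep the laboratory-flag version, but not as the only one.

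A reader might infer that the Belfast flags are wrong. The documents do not say which range is right; the fault is lack of comparability. A reader might also infer a bias between arms, because SAP 3.2 speaks of "variation in the randomization ratio across sites". No arm counts by site are given, and the SAP says that the ratio of arms 1 to 2 is similar under the planned 3:3:1 and the final 6:6:1. An imbalance at Belfast is neither shown nor excluded; the planned site check of outcome covers only daytime systolic pressure.

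**Conclusion.** The point holds as a contained defect of one descriptive safety table. That table uses two definitions of Low, and Belfast subjects with a value between 60 and 90 mL/min at either visit can fall in a different cell from identical subjects elsewhere.

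A reader might go further and conclude that the trial hides falls below 60 mL/min. The documents do not support that. Masking applies only to Belfast subjects whose baseline is 60 to 90. Falls at every other site, and Belfast falls from above 90 to below 60, appear as Normal-to-Low. A masked faller's baseline value should also appear in the report's note.

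The size of the effect is unknown. Belfast is one of the four largest recruiters among eight randomizing sites (SAP 1.3.13), but its number of subjects is not given, and the percentages above rest on assumed distributions. No hypothesis test or success criterion depends on the table.

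**What to change.** Derive the creatinine-clearance category from the numeric value with one limit for all sites, and build the by-arm shift table from that. The natural choice is ≥60 mL/min, because the SAP already uses it as the criterion for its note. It is proposed for comparability, not as a judgement on the clinically correct range. Keep the laboratory-flag version as a supplementary table or listing, with the range difference in a footnote; the text note can then be short.

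The cost is one derivation, one extra table, and a departure from laboratory-specific ranges for this one parameter. SAP v4.0 is labelled post-unblinding (SAP 1.5), so the added table should be identified as such. It introduces no newly chosen limit, since ≥60 mL/min is already in the text.

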## 12-Lead ECG

The 12-Lead ECG diagnoses will be summarized for the Safety population by a shift table presenting the number and the percentage of patients in each bivariate category (Initial Screening Visit versus Day 14) with regards to Investigator’s interpretation (Normal, Abnormal NCS, Abnormal CS, Not done) will be provided by treatment group.

## 7.10. Additional Analyses

A set of additional analyses will be performed, which will include testing of pharmacokinetics, BP at peak and trough amlodipine concentrations, sensitivity analyses, exploratory and other efficacy analyses, and Investigational Site-specific analyses.

### Pharmacokinetics

For the individual patient data listing of amlodipine plasma concentrations, all values below the LLOQ will be reported as BLQ, as in the bioanalytical report.

Non-transformed amlodipine plasma concentration values at Day 14 will be summarized for the PK population by treatment group by descriptive statistics (n, mean, SD, median, and range). A t-test will compare the non-transformed amlodipine plasma concentration values in those subjects who receive amlodipine tablets (10 mg) given alone (with matched celecoxib placebo) (arm 2) with those who receive amlodipine tablets (10 mg) and celecoxib capsules (200 mg) given together (arm 1). A box plot of the non-transformed amlodipine plasma concentrations at Day 14 by treatment arm will be produced. For these analyses, BLQ values will be treated as 0, and only treatment arms that included amlodipine will be included (i.e., the placebo + placebo arm will not be included).

Log-transformed amlodipine plasma concentration values at Day 14 will be summarized for the PK population by treatment group by descriptive statistics (n, mean, SD, median, and range). A t-test will compare the log-transformed amlodipine plasma concentration values in those subjects who receive amlodipine tablets (10 mg) given alone (with matched celecoxib placebo) (arm 2) with those who receive amlodipine tablets (10 mg) and celecoxib capsules (200 mg) given together (arm 1). For these analyses, only treatment arms that included amlodipine will be included (i.e., the placebo + placebo arm will not be included). Further, all BLQ values will be treated as 0.04 ng/mL rather than 0. Zero cannot be log-transformed. Assignment of the BLQ values to a nonzero number will allow computation of the log transformation. The selection of 0.04 ng/mL as the nonzero number for BLQ assignment was based on the LLOQ of the validated bioanalytical method (i.e., 0.05 ng/mL) and selecting the next lowest number at the hundredth decimal place.

### Peak and trough

SBP and DBP at the expected peak and trough amlodipine concentrations will be summarized for the ITT population by treatment group at Day 6 and Day 13 by descriptive statistics (n, mean, SD, median, and range). Additionally, the difference between Day 6 and Day 13 will be calculated and summarized by descriptive statistics (n, mean, SD, median, and range).

For each variable (SBP peak, SBP trough, DBP peak, and DBP trough) a comparison between treatment groups will be performed with a two-sample t-test of the change from Day 6 to Day 13. A LOCF method of imputation will not be applied for missing values. The p-value will be evaluated on a two-sided t-test.

The trough BP (SBP and DBP) is the ambulatory BP measurement taken closest to the time of study drug administration on Study Day 6 or Day 13, respectively, that is also before the time of study drug administration that day. If there is no ambulatory measurement prior to administration of study drug on Study Day 6 or Day 13, the first ambulatory measurement after study drug administration that day will be used as trough.

The peak BP (SBP and DBP) is the ambulatory BP measurement taken closest to the time point 9 hours after study drug is administered on Study Day 6 or Day 13, respectively, that is also before the time point 9 hours after the study drug is administered that day. Based on the approved labeling for amlodipine besylate tablets, the expected peak time for amlodipine is 6 to 12 hours after the medication is administered, and thus the midway point (9 hours) was selected for this analysis.

